At the present time, our offices are using outdated communication methods in an age of new technology that include text messaging, smart-phone apps, and social media. Multiple surveys have reported that patients would actually prefer digital communication from their provider. Moreover, physicians have expressed that "professional burnout" is related to excessive paperwork and generalized office inefficiencies. The best available electronic communication is email, but this becomes overbearing for office staff and patients usually have the same predictable questions. Typically, we can predict what types of questions patients will have at their respective time point after surgery.

There has been a recent surge in the development of electronic patient engagement platforms. These new technologies aim to provide patients with a new form of digital communication and optimize our delivery of healthcare information. These digital communication tools are designed to increase patient activation and promote positive patient behavior. There have been a small number of scientific studies that support their efficacy. The reported data suggests that health text messaging is a convenient way for patients to receive information, allows timely distribution of information, increases patient compliance, improves patient outcomes (medication adherence, decrease surgical infections with antiseptic showers), and can reach a large patient population, including those who are socioeconomically isolated.

This has led us to develop our proposed study, which implements an automated unidirectional electronic patient engagement tool that sends patients diagnosis and treatment specific information at the appropriate time to maximize patient outcomes. The program relies on specific SMS text messages that are less than 160 characters; packaged with instructional videos that are less than 30 seconds which demonstrate key points and proper technique for home exercises. The utility of the program is that it anticipates the most common reasons for non-compliance or readmissions in the early (<12 weeks) postoperative period and sends SMS messages to guide patients through this difficult time and prevent additional communication to the office staff and physician. We expect that the results of this study help us understand the utility of text messaging patient instructions in the postoperative period.

Study Rationale

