The effect of a digital patient engagement platform will be assessed as it pertains to the improvement in postoperative knee range of motion, office staff efficiency, and patient satisfaction following total joint arthroplasty (TJA) in the form of a total knee arthroplasty (TKA) or total hip arthroplasty (THA).

Hypothesis

The hypothesis is that following the implementation of an electronic digital patient engagement platform will improve the amount of time spent on rehabilitation activities daily, deep vein thrombosis (DVT) compliance, narcotic use, overall mood, save office staff time and resources, and improve patient satisfaction scores in a cohort of patients indicated for TKA or THA.

Study Plan

This study will be a large, prospective trial of patients undergoing TKA or THA. All patients who sign the consent will be enrolled in the study. Enrollment will continue for 150 patients, 75 in each group, where a power analysis will be performed to determine the total number to show a clinically important difference.

Enrollment Process

Patients over 18 who are determined clinically and by knee/hip radiographs to have symptomatic total joint disease, and elect to have surgery will be invited to participate in this study. Informed consent will be obtained preoperatively in the office setting. Only patients recommended to undergo TKA or THA by the treating surgeon will be offered enrollment in the study.

Eligibility

Inclusion Criteria

1. Patient scheduled to undergo a TKA or THA.
2. Written informed consent is obtained

Exclusion Criteria

1. Patients without smartphone capabilities
2. Revision surgery
3. Any patient lacking decisional capability

Study Procedures

- Eligibility - Once a patient has met the pre-operative criteria, s/he will be offered the opportunity to participate in this study.
- Patient Consent - The patient must be made fully aware of the protocol requirements and s/he must acknowledge his/her understanding and agreement by signing the informed consent and privacy statement.
- Text Messaging – 1-84messages will be sent to the patient in the initial 6-week postoperative period between the hours of 9AM and 7PM. Some messages will be associated with Internet links to instructional videos (authorized by the treating physician) for home exercises.

Timeline of Events

1. All patients will have a preoperative knee/hip radiographs.

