2. Once informed consent is obtained, the patient will be provided a one-page “diary” with areas to record the amount of time spent on rehabilitation activities daily, overall mood, narcotic use, and DVT prophylaxis compliance.
3. Patients will be randomized to either the control or experimental group. The control group will receive their post-operative instructions in the usual manner. The experimental group will receive their postoperative instruction in the usual manner but will also receive the digital text messages for the initial 6-week postoperative period.
4. If the patient is randomized to the experimental group, we will obtain their preferred cell phone number and this number will be added into the postoperative texting program algorithm.
5. The patient will then undergo surgical reconstruction in the usual manner. The text-messaging program will begin on postoperative day #0.
6. Any phone call or email from patients in the control and experimental treatment groups will be recorded by the surgeon’s office staff for data processing at the completion of the study.

7. The patients will present for the postoperative visits in the standard manner. At the 6-week post-operative visit, the patient will be prompted to return the completed one-page diary.
8. All patients will complete their prescribed physical therapy as determined by the surgeon. The physical therapy protocols will be identical for the control and experiment study cohorts.
9. At their 6-week postoperative visit, the experimental study cohort will be also be asked to fill out a 7 question survey to gather their feedback and satisfaction with the electronic postoperative text messaging program. There will also be a commentary section in the survey to allow them to provide any further recommendations or insight.

Benefits of Participation

There is no direct benefit to the patient for their participation in this study. The results will contribute to the improvement in postoperative care after total joint arthroplasty. The use of this type of electronic patient engagement protocol may improve their recovery and change the way we interact and deliver healthcare information to patients in the future. The study will help determine the extent to which patient enjoy receiving digital information in the postoperative period.

Alternatives to Participation

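### Office contacts are recorded by the staff whose workload is being measured, and the plan does not keep allocation from them, so arm-dependent recording could create or hide the hypothesised saving

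*Combined protocol and SAP*

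**What the plan says.** The Hypothesis section expects the program to "save office staff time and resources", and the Study Rationale lists office staff efficiency among the effects to be assessed. The background gives the expected direction: the messages are meant to "prevent additional communication to the office staff and physician".

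Item 6 of the Timeline of Events is the only text on how this is measured: "Any phone call or email from patients in the control and experimental treatment groups will be recorded by the". It covers both arms. The recorders it names are the staff of the surgeon's office, and the records are processed once the study has ended.

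On allocation, item 3 says "Patients will be randomized to either the control or experimental group". Controls get the usual instructions, and the experimental arm gets those plus the texts. Item 4 says that the preferred cell number is obtained for patients randomized to the experimental arm and that "this number will be added into the postoperative texting program algorithm". The item does not say whether the people who do this are also the people who log contacts.

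The documents do not describe masking of the recorders, an independent count, a definition of a countable contact, or a check that the log is complete.

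**The concern.** The recorders are the people whose workload is the measurement, and the expected direction is written into the plan. With no sham messages, allocation is not hidden by design. Staff could learn it from the texting-program enrolment or from a caller who mentions the texts. A recorder who knows the arm may decide differently whether a brief or repeat contact is worth logging.

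This comparison matters because most of the other hypothesised effects rest on patient self-report. Rehabilitation time, mood, narcotic use and DVT prophylaxis compliance come from the patient diary (item 2). The satisfaction survey goes only to the experimental arm (item 9). If contacts are logged differently by arm, a difference in the log cannot be told apart from a difference in calls and emails. Because the records are processed only when the study ends, a missed contact is unlikely to be noticed while it could still be recovered.

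**Working it through.** The plan gives no figure to reproduce here. It states 150 patients, 75 per group (Study Plan), but no contact rate, variance, significance level or effect size. The calculation below therefore shows what would follow from a given recording imbalance. It does not estimate how likely an imbalance is.

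**Inputs**
- From the plan: n = 75 per arm.
- Assumed: true mean contacts m0 = 2 or 4 per patient, the same in both arms; negative-binomial dispersion k = 0.5 or 1.0; two-sided 0.05; complete control log; a fraction u of experimental-arm contacts unlogged.

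**Formulas**
- Logged experimental mean: m1 = m0(1 − u).
- Apparent log rate ratio, in absolute value: d = −ln(1 − u).
- SE = sqrt[(1/m0 + k)/75 + (1/m1 + k)/75].
- Probability of nominal significance = Φ(d/SE − 1.96) + Φ(−d/SE − 1.96).

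**One case in full** (u = 0.2, m0 = 4, k = 0.5)
- m1 = 3.2 and d = −ln 0.8 = 0.223.
- SE = sqrt[(0.25 + 0.5)/75 + (0.3125 + 0.5)/75] = sqrt(1.5625/75) = 0.144.
- d/SE = 1.546, so the probability is Φ(−0.414) + Φ(−3.506) = 0.340.

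**All cases**

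| Unlogged, experimental arm | m0=2, k=0.5 | m0=2, k=1.0 | m0=4, k=0.5 | m0=4, k=1.0 |
|---|---|---|---|---|
| 0% | 0.050 | 0.050 | 0.050 | 0.050 |
| 10% | 0.098 | 0.082 | 0.114 | 0.089 |
| 20% | 0.263 | 0.194 | 0.340 | 0.227 |
| 30% | 0.546 | 0.406 | 0.683 | 0.481 |

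At 20% and 30%, essentially all of these rejections favour the texting arm. The formula is symmetric: the same loss in the control log alone would produce rejections at the same rate, in the other direction.

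**Sensitivity to the assumptions.** A different test (difference in mean logged contacts) over 1 to 5 contacts per patient gives these ranges for 10%, 20% and 30% unlogged:
- Overdispersed counts, k = 0.5 to 1: 7-12%, 15-36%, 31-70%.
- Poisson counts: 10-29%, 25-82%, 51-99%.

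Simulation agreed with these to within about 1 to 2 percentage points.

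**Equal losses.** If both logs lose 20%, the rate ratio is unchanged. The SE is multiplied by sqrt[(1/(0.8·m0) + k)/(1/m0 + k)]. For m0 = 2, k = 0.5 this is sqrt(1.125/1.0) = 1.06. For m0 = 4, k = 1.0 it is sqrt(1.3125/1.25) = 1.02. The loss is about 2-6% in SE, and no saving is created.

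**The case against.** The strongest reply is that this argues from silence. No sentence says that the staff who answer calls know the allocation, and the people who enter numbers under item 4 are not identified as those staff. That is correct. A reader might infer that the recorders are unmasked and will favour the texting arm, but the documents show neither. What stands is that nothing in the plan prevents them from knowing, in a trial where the design does not hide the arm.

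A reader might also infer that the log is kept by hand and that under-recording by busy staff would by itself produce a saving. The medium is not stated. Being busy does not make recording depend on arm, and losses shared equally leave the rate ratio alone. Staff gain from fewer actual contacts, not from fewer logged ones, so a motive to omit entries should not be presumed. Over-logging in the experimental arm is also possible and would hide a real saving.

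The size is conditional. It assumes a complete control log, and nothing in the documents supports any particular value of u.

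It would also be too strong to say that the trial loses its most credible comparison. No primary outcome is named, staff time is one of several hypothesised effects, and the Study Rationale also names knee range of motion, which is not a diary item.

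Finally, telephone records are not a ready answer. The documents do not say that the office keeps retrievable ones. Item 4 obtains a preferred cell number only in the experimental arm, so matching by number could identify those patients more completely than controls. This objection stands, and it shapes the fix.

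**Conclusion.** The concern holds as a weakness of design with a cheap remedy. The only stated measure of the hypothesised staff saving is recorded by the staff concerned, and allocation is not kept from them. Bias is possible in either direction and is not demonstrated.

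Under the assumptions set out above, 10% of experimental-arm contacts unlogged would raise the chance of a nominally significant result from 5% to about 8-11%. With 20% unlogged it would be about 19-34%, and with 30% about 41-68%. Wider assumptions about contact rate and dispersion widen these bands. The conclusion that the procedure should change rests on the plan's text and not on any one of these figures.

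**What to change.** - State that the staff who log contacts do not enter numbers into the texting program and do not have the allocation list or the program's enrolment list.
- Have them log against one list of all enrolled patients from both arms, with arm not shown.
- Obtain preferred telephone number and email address from every patient before randomization, so that contacts can be matched equally well in both arms.
- Where the office telephone system and mailbox keep retrievable records, have someone without the allocation match them to the full list. Use them as the source of the count, or as a completeness check on the log in both arms.

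The cost is a small reassignment of tasks and one matching step. Randomization, intervention and sample size do not change. Masking will be imperfect, because some callers will mention the texts.

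### Satisfaction is measured only in the texting arm, so the hypothesis that texting improves patient satisfaction scores cannot be tested

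*Combined protocol and SAP*

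**What the plan says.** The Study Rationale states that the platform's effect "will be assessed as it pertains to the improvement in postoperative knee range of motion, office staff efficiency, and patient satisfaction". The Hypothesis goes further and predicts that the platform will "improve patient satisfaction scores in a cohort of patients indicated for TKA or THA". Satisfaction is thus one of three effects in the Rationale and one of six in the Hypothesis (the others being rehabilitation time, DVT compliance, narcotic use, mood, and office staff time and resources).

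The design is comparative. Under Timeline of Events, item 3, "Patients will be randomized to either the control or experimental group", and the Study Plan sets 75 patients per group.

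Satisfaction is collected in one place, Timeline of Events, item 9. At the 6-week visit, "the experimental study cohort will be also be asked to fill out a 7 question survey to gather their feedback and satisfaction". What the survey asks about is "satisfaction with the electronic postoperative text messaging program", together with a space for comments. Item 9 gives no corresponding form to the control group.

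**The concern.** To say that scores improve is to make a comparison, either with patients who did not receive the texts or with the same patients beforehand. The plan randomises patients, which would support the first kind of comparison, but it then collects the outcome in one arm only.

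There is also a difference of construct. The Hypothesis concerns the satisfaction of surgical patients, whereas the survey concerns a texting service that control patients never receive. Handing the same survey to controls would not solve the problem.

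A high average rating from the experimental arm could be presented as support for the Hypothesis when it says nothing about whether those patients are more satisfied than they would have been under usual instructions. The gap cannot be repaired at analysis. Once the 6-week visits have passed, the control scores are lost.

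**Working it through.** **Step 1. Look for a comparator.** Each data-collection step under Timeline of Events was checked for content and arm.

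| Item | What is recorded | Control | Experimental | Satisfaction measured? |
|---|---|---|---|---|
| 2 and 7, diary | "areas to record the amount of time spent on rehabilitation activities daily, overall mood, narcotic use, and DVT prophylaxis compliance" | yes | yes | no |
| 6, office contacts | "Any phone call or email from patients in the control and experimental treatment groups will be recorded by the surgeon’s office staff" | yes | yes | no |
| 9, survey | feedback on the texting program, 6 weeks | no | yes | yes, program-specific |

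That the diary goes to both arms is inferred from its being handed out in item 2, before randomisation in item 3. Mood cannot stand in for satisfaction, because the Hypothesis lists the two as separate effects.

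**Step 2. Count the observations.** With 75 per group (Study Plan) and full return, there are 75 satisfaction scores in the experimental arm, 0 in the control arm and 0 before the intervention. The between-arm difference needs a control mean, and the within-arm change needs a baseline mean. Neither exists, so neither quantity nor its standard error can be estimated. Enlarging the trial does not change this.

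**Step 3. What the planned survey can deliver.** The document gives no scoring format, expected result or return rate. Assume, for illustration, that a question is summarised as the proportion satisfied and that all 75 surveys come back. The 95% confidence half-width is 1.96 × √(p(1−p)/75):

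- p = 0.7: 1.96 × √(0.21/75) = 0.104
- p = 0.8: 1.96 × √(0.16/75) = 0.091
- p = 0.9: 1.96 × √(0.09/75) = 0.068

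The plan would therefore yield a one-arm proportion known to within about 7 to 10 percentage points, with nothing to compare it with.

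**Step 4. What a two-arm measure would deliver.** The document states no significance level, power, effect size, SD or dropout, so there is no planned calculation to reproduce. Assume a continuous score and a two-sided 5% level. The detectable standardised difference is (z for 1−α/2 + z for power) × √(2/n), with n per arm:

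- n = 75, 80% power: (1.960 + 0.842) × √(2/75) = 0.457 (0.460 by the t-test)
- n = 75, 90% power: (1.960 + 1.282) × √(2/75) = 0.529
- 10% missing, n = 67.5, 80% power: 0.482
- 20% missing, n = 60, 80% power: 0.511

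Read the other way, 75 per arm gives power of about 0.45, 0.69 and 0.87 for true differences of 0.3, 0.4 and 0.5 SD. The existing sample could detect a moderate effect on satisfaction, if satisfaction were measured in both arms.

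**The case against.** The strongest reply is that the survey was never meant as a comparative outcome. Benefits of Participation says the study should help show how much patients like getting information digitally. A survey of the texted patients serves that aim well and needs no control group. On this reading the mismatch is confined to one clause of the Hypothesis and one term of the Rationale, satisfaction comes last in both lists, and the diary items and office contacts can still be compared between arms. This stands in part: the survey is useful for that descriptive purpose and should be kept. It does not rescue the Hypothesis, which separately predicts better satisfaction scores. Nor does the available text name a primary endpoint that would rank satisfaction below the other effects.

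Three further points are fair.

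- The Rationale sets out to assess improvement in satisfaction, and only the Hypothesis predicts it.
- Neither the survey nor the diary form is reproduced, so the finding is limited to the text available. Item 9 nevertheless assigns the survey to the experimental cohort, and nothing in that text suggests a control score.
- Control patients know they received no texts, so even a two-arm satisfaction comparison would be unblinded self-report and open to expectation bias. The same is true of the trial's diary outcomes. It is a reason for neutral wording and cautious interpretation, not for leaving controls unmeasured.

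**Conclusion.** The concern holds. As written, the plan provides no control score and no baseline score for satisfaction, so the hypothesised improvement cannot be estimated or tested at any sample size. This conclusion follows from the described data collection alone and depends on no numerical assumption. The confidence half-widths and detectable differences are illustrations that rest on the assumed score type, significance level, power and return rates.

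The defect is limited to satisfaction. It warrants correction before patients reach their 6-week visits, because the missing data cannot be recovered later and a stated hypothesis would otherwise go unanswered.

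**What to change.** Amend Timeline of Events, item 9, so that both arms complete the same short satisfaction form at the 6-week visit. The questions should cover matters that every patient experiences, such as postoperative instructions, communication with the office and overall care, and should not mention texting. Choose the form and its scoring in advance, compare the score between the randomised groups, and report the number returned in each arm. No baseline score is needed, since randomisation supplies the comparison. State where satisfaction ranks among the six hypothesised effects, because it adds one more comparison to a plan that names no primary endpoint. Keep the 7 program questions as a separate descriptive summary for the experimental arm, completed after the common form so that they do not colour the answers to it.

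If this is not wanted, remove the satisfaction claim from the Hypothesis, align the Rationale, and describe the survey as acceptability feedback.

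The cost of the first route is one extra page per patient at a visit where the diary is already being returned, some work to choose and score the form, and a protocol amendment with ethics review. No additional visit is needed. The second route costs only an edit to the text, but gives up a stated aim.
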